4.6.2.5 Therapy Stopping Points

As indicated previously, the study will be halted and re-evaluated by the DSMB if any patient in the study group develops thrombosis of the allograft, thromboembolic events (TE) or evidence of coagulation abnormalities that would suggest impending TE. In addition, the study will be halted or stopped if any other known or unexpected AEs attributable to C1-inhibitor occur. Reassessment of the study goals and complications will be done and discussed with the DSMB prior to proceeding. A summary report will be submitted to the IRB and FDA.

4.6.2.6 Primary Safety Endpoints

- Overall incidence of adverse events and serious adverse events and relationship to the study treatment including but not limited to, occurrence of infections, thrombosis of the allograft, vascular thromboses, bleeding, death, vital signs, and abnormal lab values.

4.6.2.7 Secondary Safety Endpoints

- Chemistry and coagulation parameters
- eGFR at 1M, 3M, 6M
- Patient survival at day 180
- Graft survival at day 180
- Rate of acute cellular and antibody mediated rejection episodes at day 180
- Rate of de novo Donor Specific Antibody (DSA) development

4.6.3 Assessment Periods

4.6.3.1 Screening Procedure -Day 0

Prior to screening activities, each patient must be given an opportunity to ask questions and to understand the details of study participation. This consent process must be documented in the patient's source documents and evidenced by the patient signing the informed consent form.

After signing the ICF, each patient will be assigned a patient identifier number that will be used on all subject documentation. Numbers will be assigned in ascending sequential order. This number will also correspond to the patient number entered on study materials.

The Principal Investigator or qualified and assigned Sub-investigator will review the inclusion and exclusion criteria and laboratory test data to confirm eligibility of each subject.

The screening procedures will include the following:

- Informed consent
- Medical history
- Inclusion/Exclusion criteria review
- Vital signs/weight
- Complete physical examination
- Hematology & chemistry profile
- Record PT, PTT, INR collected by SOC
- Review historical serologies for HIV, HBV, HCV, CMV and EBV, collected by SOC
- Concomitant medications
- Review of previous Pneumococcal vaccination
- Review of Pregnancy test (for WOCP, Age 12-55 years old)

4.6.3.2 Day 0 – Day of Transplantation

- Vital signs (pre- and post-transplant)
- Physical examination (pre- and post-transplant)
- Randomization (pre-transplant)
- Hematology & chemistry profile (pre- and post-transplant)
- Record PT, PTT and INR collected by SOC (pre-transplant)
- Concomitant medications (pre- and post-transplant)
- ECG (pre-transplant)
- Chest x-ray (pre-transplant)
- Serum Creatinine (pre-and post-transplant)
- Berinert vs. Placebo infusion (on call to OR) with heparinated saline
- Campath 1H or Thymoglobulin administration
- Assessment of implantation biopsy (if collected)
- Urine output measurement if producing urine (post-transplant)
- Adverse event assessment
- Dialysis assessment

4.6.3.3 Day 1-7 Assessments measured on days 1, 3 and 7 (or until discharge)

- Concomitant medications
- Serum creatinine measurements through Day 7 or until discharge.
- Dialysis assessment
- Physical examination
- Vital Signs/weight
- Calculated estimated GFR
- Record Urine output measurement if producing urine
- Adverse event assessment
- Hematology & chemistry profile
- Urinalysis if producing urine. Urinary IL-18 to be collected on two days, between day 1 to 7, if producing urine and testing is available

4.6.3.4 Day 30 ± 7 days

- Concomitant medications
- Physical examination (may occur as a video visit)
- Vital Signs/weight
- Dialysis assessment
- Adverse Event Assessment
- Calculated estimated GFR
- Hematology & chemistry profile
- Urinalysis

4.6.3.5 Days 90, 180 ±30 days

- Concomitant medications
- Physical examination (may occur as a video visit)
- Dialysis assessment
- Vital Signs/weight
- Adverse Event Assessment
- Calculated estimated GFR
- Hematology & chemistry profile
- Urinalysis
- ACR assessment on Day 180
- Assessment of SOC biopsies on Day 180
- Patient survival assessment on day 180
- Graft survival assessment on day 180
- Donor Specific Antibody (DSA) assessment at Day 180

4.6.4 Observations And Measurements—see Appendix A.**4.6.4.1 Physical Examination**

A complete physical examination will include; the examination of the following body systems: general appearance, skin, HEENT (head, ears, eyes, nose, throat), cardiovascular, pulmonary, abdomen, neurological, lymph nodes, spine and extremities (skeletal). Patient visits may occur as video visits with the MD as per standard of care procedures.

4.6.4.2 Vital Signs

Vital signs; including blood pressure, heart and respiratory rate will be measured using clinically acceptable methods and devices at each clinic visit. Height will be measured at the screening visit only.

4.6.4.3 Serum Creatinine

Serum creatinine levels will be measured per institutional SOC.

4.6.4.4 Calculated GFR

Estimated GFR will be calculated using the MDRD formula.

4.6.4.5 Urine Output

Urine output will be collected and recorded for the first 0-7 days post-transplant, until patient discharge.

4.6.4.6 PT, PTT and INR Tests

PT, PTT and INR tests will be performed per institutional SOC.

4.6.4.7 Hematology and Chemistry Profile

Hematology and Chemistry profile performed per institutional SOC

4.6.4.8 ECG Testing

An ECG will be performed per institutional SOC.

4.6.4.9 ACR Assessment

An acute rejection assessment will be recorded on patients who were diagnosed with an ACR grade \geq Grade 2 per the Banff grading system and received anti-rejection therapy.

4.6.4.10 Rate and Duration of Dialysis

Duration of dialysis will be measured by the number of sessions of dialysis treatment needed in the first 30 days post transplant. As for rate of dialysis, one dialysis session will represent the need for dialysis treatment.

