1.0 Introduction

Delayed graft function (DGF), defined as the need for dialysis in the first week after kidney transplant, is estimated to occur in over 20% of deceased donor kidney transplants (1). Its development is associated with an increased risk of rejection, poorer long-term kidney allograft function, and lower patient and graft survival (2,3). This association is modified by the severity of DGF, as indicated by the duration of dialysis-dependence after transplant, where longer periods of dialysis-dependence are associated with progressively higher risks of rejection and graft failure (4). Not surprisingly, kidneys at higher risk for DGF are more likely to be discarded in the United States despite the well-documented shortage in donor organ supply (5,6).

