1.1 Criteria for Defining IRI/DGF in Human Kidney Transplants

Historically DGF has been defined as the requirement for dialysis during the first week after renal transplantation, however the postoperative requirement of hemodialysis or peritoneal dialysis is not standardized and the decision to dialyze varies from center to center and among consultants (14). Efforts have been made to scientifically quantify DGF in a more stringent manner with various alternative definitions of DGF including; (14) the number of days to achieve a creatinine clearance of >10 mL/min, calculated by the Gault-Cockcroft formula (15) a serum creatinine level of >3 mg/dL on the fifth day post-transplant (16) the need for dialysis within 72 hours after transplantation (17) serum creatinine level changes, including an increase, remaining unchanged, or decreasing by less than 10% per day immediately after surgery during three consecutive days for >1 week (18) a rising serum creatinine level above that before surgery, or urine output of <300 mL within 6 hours of transplantation, despite diuretics and adequate volume (19) urine output of <1 L in the first 24 hours or a decrease in serum creatinine of <20 –30% reflected in a poor glomerular filtration rate (GFR) (20) and calculating the creatinine reduction ratio on day two following surgery (21). However, despite these alternative suggestions, the conventional definition of “requirement for dialysis in the first week post-transplant” remains the most utilized and published definition for DGF, with “need for dialysis” being easily measured and clinically relevant. However, recent data from the FDA indicate that more relevant end points for clinical trials of agents aimed at reducing IRI/DGF would be need for dialysis in the first month post-transplant and eGFR at 1 year (<https://www.fda.gov/media/103928/download>).

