1.5 Evidence for Efficacy of C1INH in Preventing IRI/DGF in Human Kidney Transplant Recipients

C1 esterase inhibitor was approved by the United States Food and Drug Administration in 2009 for the treatment of hereditary angioedema. C1 esterase inhibitor is a serine protease inhibitor targeting C1s and C1r in the classical pathway and MASP-1 and MASP-2 in the MBL complement pathway and is therefore a relevant intervention to test the impact of complement inhibition on short- and long-term kidney function among allografts with ischemia-reperfusion injury. Our group recently reported twelve-month outcomes of a double-blind, randomized, placebo-controlled study investigating the safety and efficacy of C1 esterase inhibitor among deceased donor kidney transplant recipients at high-risk for DGF (25). Salient findings from this study were a shorter duration of DGF and higher estimated glomerular filtration rate (eGFR) at twelve months among patients treated with C1 esterase inhibitor compared to placebo. From our initial report we showed that C1INH was associated with a ~50% reduction in need for dialysis in the first month post-transplant in high risk patients and a clinically significant improvement in eGFR at 1 year. This is shown in

CONFIDENTIAL

C1INH (Berinert®) IRI Study in Kidney Transplant

figure 6 below. For more details please see the referenced manuscript that is attached as an appendix.

[figure not shown]

Figure 6: This figure demonstrates that giving C1INH 50U/kg at time of transplant and @24 hrs post-transplant was associated with a near significant reduction in need for dialysis during the 1st month post-transplant and a significant improvement in eGFR at 1 year compared to placebo. The at risk population was balanced for risk factors associated with IRI/DGF being enriched for the risk. This data would suggest that prevention of early IRI/DGF has long-term implications for improving kidney function.

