- Patients with a history of thrombosis or hypercoagulable state, excluding access clotting.
- Patients with a history of administration of C1INH containing products or recombinant C1INH within 15 days prior to study entry.
- Patients with a known hypersensitivity to treatment with C1INH.
- Patients with an abnormal coagulation function. (INR >2 , PTT > 50 , PLT $<60,000$) who are not on anti-coagulation.

	
6) Patients with known active presence of malignancies.
 
7) Patients who are PCR positive for Hep B, Hep C, or HIV.
 
8) Recipients of pre-emptive kidney transplantation (unless baseline SCr is ≥ 4 mg/dL, making minimal urine output)
 
9) All zero mismatch kidneys.
 
10) Recipients of multi-organ transplants. (kidney and any other organ)
 
11) Recipients of kidney allograft that was arriving on pump preservation
 
12) Recipients of kidney allograft from a living donor.
 
13) Female subjects who are pregnant or lactating.

STUDY ENDPOINTS	
SAFETY:
 
 Overall incidence of adverse events and serious adverse events and relationship of AE and SAEs to the study treatment Need for HD in the 1st month post-transplant. eGFR at 1M, 3M, 6M Patient and graft survival at Day 180 Rate of acute cellular rejection (ACR) and antibody mediated rejection at 6M 
EFFICACY ASSESSMENTS:
 
Primary Endpoints
 
Need for Dialysis in the 1st Month Post-Transplant: (Excluding patients who get dialysis for hyperkalemia)
 
 The proportion of patients enrolled who require at least one session of dialysis in the first 30 days post transplant. Number of dialysis sessions per patient in the first 30 days post transplant. 
Renal Function and Graft Survival 6M
 
 eGFR at 6M post-transplant Patient & Graft survival 6M post-transplant 
Secondary Endpoints
 
 Rate of acute cellular and antibody mediated rejection episodes by day 180 Calculated creatinine clearance at 1M, days 90, 180days post transplant. Development of DSAs at 6M SOC biopsies will be assessed at time of implantation and 6M post implantation.
IMUNOSUPPRESSION REGIMEN	
 Induction therapy using Thymoglobulin in divided doses (total of 6mg/kg) or Campath 1H 30mg SQ x 1. Calcineurin inhibition (Tacrolimus or Cyclosporine) will be initiated as per standard practice

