4.2.1 Inclusion Criteria

Recipient Inclusion Criteria

- 1). Adult men or women (18-77 years of age) who are on chronic dialysis therapy and acceptable candidates for kidney transplant.
- 2). Understand and sign a written informed consent prior to study specific procedures.
- 3). Recipients who are ABO compatible with donor allograft. (A2 to B offers allowable)
- 4). AND one of the below criteria:
 - a) Recipients of kidney allograft from **KDPI >80** donors
 - b) Recipients of kidney allograft from DCD donors
 - c) Recipients of kidney allograft with CIT > 24 hours
 - d) Recipients of kidney allograft from donor on HD/CRRT prior to death/procurement
 - e) Recipients of kidney allograft with donor terminal creatinine SCr ≥ 3.0 mg/dL
- f) Patient risk a total risk index score of ≥ 3 based on the following:

Table 1. Characteristics	Risk Index
Donor Age (years)	
<40	0
41-49	1
50-54	2
55-59	3
>60	6
Cold Ischemia Time (hours)	
0-12	0
13-18	1
19-24	2
24-30	3
31-36	4
>37	6
Recipient Race	
Non-black	0
Black	1
Recipient with Diabetes	
Has diabetes	1
Donor cause of death due to CVA	
Donor age >50 years	3
Donor Terminal Cr	
TCr >4	3
TCr $\geq 2-4$	2
Tcr <2	0

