4.6 Study Variables

4.6.1 Efficacy Variables

4.6.1.1 Primary Efficacy Endpoints

For patients who require dialysis in the first 30 days: (Excluding patients who get dialysis for hyperkalemia)

- The proportion of patients enrolled who require at least one session of dialysis in the first 30 days post transplant.
- Number of dialysis sessions per patient in the first 30 days post-transplant.

Renal function and graft survival 6M

- **eGFR at 6M post-transplant**
- **Patient and graft survival at 6M post-transplant**

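### Section 4.6.4.10 measures dialysis duration by counting sessions: keep the count as dialysis burden, and define duration separately from dated treatments with a rule for early death

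*Combined protocol and SAP*

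**What the plan says.** Section 4.6.4.10 gives the operating rule: "Duration of dialysis will be measured by the number of sessions of dialysis treatment needed in the first 30 days post transplant". The same count appears among the primary efficacy endpoints in section 4.6.1.1, where it is named for what it is: "Number of dialysis sessions per patient in the first 30 days post-transplant".

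The rationale is written in terms of time. Section 1.0 grades the severity of delayed graft function (DGF) by time on dialysis: "as indicated by the duration of dialysis-dependence after transplant, where longer periods of dialysis-dependence are associated with progressively higher risks of rejection and graft failure". Section 1.5 lists among the earlier trial's main findings "a shorter duration of DGF and higher estimated glomerular filtration rate (eGFR) at twelve months".

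Dialysis practice and modality are left open. Section 1.1 says, as general background, that "the postoperative requirement of hemodialysis or peritoneal dialysis is not standardized and the decision to dialyze varies from center to center". Section 4.2.1 admits adults "who are on chronic dialysis therapy and acceptable candidates for kidney transplant", and section 4.2.2 does not exclude peritoneal dialysis. In the synopsis (section 2.2) the safety list has "Need for HD in the 1st month post-transplant", while the efficacy list refers to dialysis in general.

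The documents do not define a session, do not ask for the date of each treatment, and do not say how a death before Day 30 enters the count. The one stated exclusion from the dialysis endpoints is dialysis for hyperkalemia. Section 6.1, as supplied, has no text under its heading, and the synopsis promises only descriptive and comparative statistics, so no summary measure or test is named for the count.

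**The concern.** A number of sessions is roughly time on dialysis multiplied by treatment frequency. Two patients whose grafts take equally long to recover can have different counts because they are dialyzed by different modalities or at different intervals. Two patients with the same count can have their last treatment weeks apart. If the count is reported as duration, readers will take it as evidence on the quantity that sections 1.0 and 1.5 link to prognosis, and it is not a direct measure of that.

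Death raises a second issue. A patient who dies in the first days stops accruing sessions and receives a low, apparently favorable score. Nothing in section 4.6.1.1 or 4.6.4.10 prevents this or links the count to survival.

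A related wording point affects who is counted. Read literally, a patient dialyzed only by peritoneal dialysis is a case in the synopsis efficacy list and not in its safety list.

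**Working it through.** The documents give no figure for this endpoint, so there is none to reproduce. The check is direct arithmetic; treatment schedules are assumptions and are marked as such.

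**Inputs from the documents**
- 20 patients per arm (section 4.5.7).
- 40-50% DGF expected (section 4.5.1).
- 30-50% reduction in DGF predicted (section 4.5.7).
- 30-day window (sections 4.6.1.1 and 4.6.4.10).

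**Assumed inputs**
- Hemodialysis three times a week; peritoneal dialysis once daily, each day counted as one session.
- 3 to 6 sessions per dialyzed patient.
- The arm mean as the summary.

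**1. Same dependence, different modality**
- 30 days on hemodialysis: 30 × 3/7 = 12.9, about 13 sessions.
- 30 days on daily peritoneal dialysis: 30 sessions.
- Shift in a 20-patient arm mean from one such patient: (30 − 12.9)/20 = 0.86 sessions.
- For 7 days of dependence: 7 × 3/7 = 3 against 7, a shift of (7 − 3)/20 = 0.20.

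The introductory line of section 4.6.1.1 could be read as restricting the count to dialyzed patients. With 40-50% of 20 dialyzed, that is 8 to 10 patients per arm, and the 30-day shift becomes 17.1/10 = 1.7 to 17.1/8 = 2.1.

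**2. Scale against the predicted effect**
If treatment changes only the proportion dialyzed, the expected difference in mean sessions over all 20 patients is (control proportion) × (relative reduction) × (sessions per dialyzed patient):
- Lowest: 0.40 × 0.30 × 3 = 0.36.
- Highest: 0.50 × 0.50 × 6 = 1.50.

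The 0.86 shift from one patient on daily peritoneal dialysis for the whole window lies inside this range. The 0.20 shift from a one-week course lies below it.

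**3. Same count, different timing**
Four sessions on Days 1, 2, 3 and 4, or on Days 2, 9, 17 and 26, both score 4. The last treatment falls on Day 4 or Day 26, and 26/4 = 6.5.

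**4. Early death**
A patient who dies on Day 5 after 2 sessions scores 2, better than a survivor who has 6. Against a survivor dependent to Day 30 on thrice-weekly hemodialysis, a patient who dies after 2 sessions lowers the arm mean by (13 − 2)/20 = 0.55.

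**The case against.** The strongest reply is that the primary endpoint is not mislabeled. Section 4.6.1.1 calls it a number of sessions, which is a legitimate measure of dialysis burden, and the word duration is attached to it only in section 4.6.4.10. The count also has a precedent: the earlier trial's abstract in Appendix B reports significantly fewer sessions at 2 to 4 weeks (P = .0232). Replacing it would give up comparability with that result. This stands, and it is why the count should be kept.

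A reader might infer that equal counts can stand for 4 or 26 days of dependence. The documents do not support that. The schedule in step 3 is invented, and it has gaps of 7 to 9 days between treatments, so it need not be continuous dependence. It shows only that the count carries no information on timing.

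A reader might also infer that one peritoneal dialysis patient will drive the comparison. That needs daily treatment for most of the window and a mean as the summary. The plan names no summary, and a rank-based one would blunt a single high value. The documents do not say how often peritoneal dialysis is used after transplant at this center. The trial is single-center, randomized and double-blind, so differences in modality and prescribing should add noise, not systematic bias.

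Early death may be rare. In the earlier 70-patient trial the three deaths over 3.5 years occurred at 2-3 years (section 1.5 and Appendix B). Survival at 6 months is a separate primary efficacy endpoint, so a death would be visible. It would still enter the session count as a low score.

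Finally, time to last dialysis has its own weakness: a single isolated session on Day 26 scores 26, worse than ten sessions ending on Day 20. That argues for reporting both measures.

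**Conclusion.** The concern holds in a limited form. The rule in section 4.6.4.10 does not measure the duration of dialysis dependence on which sections 1.0 and 1.5 rely, and no other section supplies a time-based measure, a modality rule or a rule for death before Day 30. One patient dependent for 30 days on daily peritoneal dialysis instead of thrice-weekly hemodialysis would move a 20-patient arm mean by 0.86 sessions; a 7-day course would move it by 0.20. Both figures rest on assumed schedules and on a mean.

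The documents do not support the stronger conclusion that the primary session count is invalid or must be replaced, or that the comparison between arms is biased by modality. The primary objective is safety, and sections 4.5.1 and 4.5.7 say the design is not powered for a difference in DGF. The change is a cheap improvement that the sponsor should make; the trial can be interpreted without it if sessions are reported as sessions.

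**What to change.** - **Section 4.6.1.1:** keep the 30-day session count as a measure of dialysis burden. Report deaths before Day 30 beside it, give the count by modality, and add a sensitivity analysis that ranks early deaths worst.
- **Section 4.6.4.10:** stop calling the count duration. Define duration separately as days from transplant to the last dialysis of any modality within 30 days, 0 if none, with the same hyperkalemia exclusion as the other dialysis endpoints. Assign 30 days to patients who die, lose the graft or are still on dialysis at Day 30. Label the measure as including death and graft loss, and report those events beside it.
- **Data collection:** record the date and modality of each treatment on the dialysis assessment already scheduled in Appendix A. Dates also fix the window, because the Day 30 visit may fall anywhere from Day 23 to Day 37.
- **Synopsis:** reconcile the hemodialysis wording in the safety list with the dialysis wording in the efficacy list. Check the result against sections 4.6.2.6 and 4.6.2.7, which do not list a dialysis endpoint.

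The cost is a little extra data entry and one more dialysis measure, which is correlated with the count and can be driven by an isolated late session. Comparability with the earlier trial's session counts is kept, and patient care does not change.
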